Sixty fathers, their female co-parent and youngest child will be recruited to participate in the study. At the time of intake at Westcare's Emerge Program and Salvation Army's Residential Substance Abuse Rehabilitation Program, fathers will be provided flyers about the study. Men who express an interest in participating in a parenting program as part of their treatment will fill out an initial interest form with their counselors (including their name, arrival and discharge date, information about how often they're in contact with their children) and have their counselors submit this form to the Project Coordinator. The Project Coordinator will schedule a screening with the potential participant and will be asked to sign a consent form,

and to sign a release of information to review their SA treatment and criminal history. Men will be told that his questionnaire and records will be reviewed and will be contacted further if considered eligible by the PI based on the study's requirements.

This will provide the opportunity to contact the mother to conduct a phone screening in regards to IPV history and willingness to participate. If the mother indicates an IPV history that involved hospitalization or strangulation or a current full no contact protective order, he will be notified that based on the demographic screening, he is not eligible for the study. If the father is eligible and agrees to participate in the study, the research assistant will contact the father to set up a baseline assessment and the co-parent will be contacted to set up a baseline interview by phone or in-person if she wants to participate. If the father is not eligible for the program we will remove the bottom portion of his screening form that includes personal information (name, arrival and discharge date, and WestCare or Salvation Army counselor information) and shred it. The top portion including de-identified information (IPV history and contact with children) will be kept to keep track of the number of referrals compared to the number of participants in the program.

Mothers of the father's youngest child will be recruited in several ways:

1. When she visits the facility she will be approached by study staff in person.
2. She will be mailed study flyers asking her to contact the research office.
3. Westcare or Salvation Army staff will call mothers and ask permission for study staff to contact them to tell them about the study.

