Following completion of baseline assessments, subjects will be randomly assigned to the FFC intervention or the Parenting Education (Dads 'n' Kids) condition. To increase the likelihood that treatment groups are balanced with respect to demographic variables, and moderators, subjects will be assigned to treatment conditions through urn randomization using a Microsoft Access-based program. In urn randomization, an algorithm modifies ongoing randomization probabilities based on prior composition of treatment groups and maximizes multivariate equivalence of groups

Fathers in each treatment group will meet individually with their assigned therapist once per week for 50-60 minutes of treatment. The Fathers for Change Intervention has three phases: individual focused, co-parent relationship focused and restorative parenting focused. Beginning with motivational interviewing, the clinician and father will discuss child development, the impact of SA and violence on parenting, and the father's own childhood experiences of SA and violence and how he would like things to be different for his own children. The clinician will also provide skills training to reduce hostile cognitions and increase emotion regulation skills. In co-parenting focused sessions the clinician will teach communication and problem solving skills, these topics will be addressed with or without the co-parents participation. In family sessions the clinician focuses on restorative parenting to

rebuild the father-child relationship. These phases can be delivered either individually to the father or together with his children present. The decision whether family members are invited to participate will be made on a case by case basis dependent on safety of the co-parent and child, their wish to participate and their ability to come to the treatment facility.

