The Dads n' Kids (Parenting Education-PE) Program will provide individual sessions only. PE was developed to provide parent education and support that is typically available to SA parents at risk for child maltreatment. This program was selected as the comparison condition because PE and FFC are equivalent in terms of treatment dose, duration, client expectation for a parenting intervention, and formation of a helping alliance with a caring professional. The clinician will provide assistance in solving problems related to family basic needs (e.g. health care, child care, housing and education). The clinician will also provide topic pamphlets that will focus on creating routines and rituals, ages and milestones to be aware of, alternative to spanking, and nutrition/fitness. The intervention is a behaviorally focused intervention to build parenting skills.

Participants in both groups will be asked to complete a baseline interview once they have been enrolled in one of our programs. Short, monthly interviews will take place to assess the client's motivation to change and working alliance with their assigned clinician. The research assistant will also conduct three post-assessment interviews: 1. Post-residential interview at 12 weeks; 2. Post-intervention interview at 16 weeks; and 3. A 3-month follow-up interview at 24 weeks from baseline. Co-parents will be asked to complete a baseline assessment and a 3-month follow-up assessment.

A complete list of study measures are outlined in Table 1. Fathers will meet in a confidential office to complete study measures that will be administered in interview format. Following administration of paper and pencil measures, fathers will complete the Articulated Thoughts in Simulated Situations Task. They will listen to audio recorded scenarios and vocally speak their thoughts into an audio recorder. Their statements are transcribed for coding by trained, blind coders. Upon completion of hearing these potentially stressful scenarios, research assistants will guide participants through a debriefing relaxation exercise of guided imagery and deep breathing to ensure men are calm prior to leaving the assessment session. We have successfully used all the included measures in prior studies with the target population without any adverse events.

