Table 1. Standardized Measures and administration for Randomized Trial

Instrument	Rater	Reliability	Base-line	Monthly During Intervention	Post Residential Intervention 12 weeks	Post Intervention 16 weeks	3 month follow-up 24 weeks
SA Outcomes							
Timeline follow-back for SA	Father and Mother	.91		X	X	X	X
Urinalysis Drug Panel	Father	NA	X	X		X	X
IPV Outcomes							
Conflict Tactics Scale Revised (CTS2)	Father and Mother	.79 to .95	X				X
Timeline follow-back for IPV	Father and Mother	.91		X	X	X	X
Court and Arrest Records	N/A	N/A	X				X
CM Risk Outcomes							
Parental Reflective Functioning Questionnaire (PRFQ)	Father	.82	X			X	X
Adult Adolescent Parenting Inventory (AAPI)	Father and Mother	.74 to .98	X			X	X
Father-Child Free Play coded using (CIB)+	Blind Coders						X
Quality of Co-Parental Relationship Scale	Father and Mother	F: .66 - .88 M: .80 - .83	X			X	X
Satisfaction Outcomes							
Client Satisfaction Questionnaire 8	Father	N/A				X	
Mediators							
Articulated Thoughts in Stimulated Situations (ATSS) and HR/SC	Blind Coders	N/A	X		X		
Difficulties in Emotion Regulation Scale (DERS)	Father	.93	X		X	X	X
State-Trait Anger Inventory (Staxi)	Father	.84 - .93	X		X	X	X
Rumination-Reflection Scale (ARQ)	Father	.88 - .91	X		X	X	

Working Alliance Inventory	Father and Clinician	.79 - .97		X			
Motivation to Change (URICA-DV)	Father	.85 - .87		X			
Moderators							
Childhood Trauma Questionnaire	Father	.80 - .97	X				
Self-Report Psychopathy Scale 3	Father	.60	X				
Life Change Index Scale	Father	N/A	X				X
Brief Symptom Inventory (BSI)	Father	.74 - .89	X			X	X
Addiction Severity Index	Father	.89	X				
Father Interview	RA	N/A	X			X	X
Treatment Services Review	Father	N/A				X	X
PhenX Measure: Self-Report HIV Testing	Father	N/A	X				
FRPN FATHER ENGAGEMENT SCALE_v1	Father	N/A				X	X
FRPN FATHER ENGAGEMENT SCALE_v2	Father	N/A				X	X
FRPN FATHER ENGAGEMENT SCALE_v3	Father	N/A				X	X
Measure of Contact-Fatherhood Research and Practice Network	Father	N/A				X	X
Domestic Violence Quiz	Father	N/A	X		X		
Co-Parenting Quiz	Father	N/A	X		X		

At the 3 month follow-up, fathers will be asked to attend a play assessment with their child. This will be a 30 minute appointment in which they will play with toys or games with their child for 15 minutes, clean up and then complete several puzzles with their child. These session will be audio recorded and coded using the Child Interactive Behavior Rating Scale by trained blind coders.

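### Five instruments filed as moderators in Table 1 are first measured at week 16, so they can only be post-treatment measures, and no baseline covariate is planned for engagement and contact

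*Protocol*

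**What the plan says.** The Study Design section of the protocol says of the measures: "A complete list of study measures are outlined in Table 1". The Moderators block of that table has 14 rows. Nine carry a baseline mark. The other five are marked at weeks 16 and 24 only: "Treatment Services Review", "FRPN FATHER ENGAGEMENT SCALE_v1" with its versions 2 and 3, and "Measure of Contact-Fatherhood Research and Practice Network".

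On timing, the same section says: "Following completion of baseline assessments, subjects will be randomly assigned to the FFC intervention or the Parenting Education (Dads 'n' Kids) condition". Week 16 is defined there as the interview after the intervention ends. The urn procedure is meant to produce groups "balanced with respect to demographic variables, and moderators", but the variables that enter the urn are not listed.

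Some information on contact is collected before randomization. The interest form completed with the counselor includes "information about how often" the man is in touch with his children. The inclusion criteria in Study Design accept fathers who lived with the child, fathers with contact as infrequent as monthly, and men expecting a first child. The separate list under Study Population sets no contact threshold.

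The SAP assigns secondary outcomes measured only at the end of treatment or follow-up to generalized linear models. It assigns outcomes measured two to five times from randomization to GEE, with a test of difference in rate of change. Facility and treatment are dummy coded. No baseline covariate is named and no moderator analysis is described.

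**The concern.** A moderator has to be fixed before treatment starts. Fathers for Change works on the father-child relationship and may bring children and co-parents into sessions, whereas the parent education arm is delivered to the father alone. Engagement and contact at week 16 could therefore be changed by allocation itself, and the table heading does not match what the schedule can deliver.

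If these scales are outcomes instead, they depart from the pattern of the trial's other parenting questionnaires. The reflective functioning, parenting inventory and co-parental relationship scales all have baseline, week-16 and week-24 administrations. Men enter with very different amounts of prior contact. With about 30 per arm, part of any week-16 or week-24 difference could be a difference present on entry, and the plan names no variable to correct for it.

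**Working it through.** **Schedule check.** Rows under Moderators in Table 1:

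| Administration | Rows | Count |
|---|---|---|
| Baseline only | Childhood trauma, psychopathy, addiction severity, HIV testing | 4 |
| Baseline and later | Life change, BSI, Father Interview, Domestic Violence Quiz, Co-Parenting Quiz | 5 |
| Weeks 16 and 24 only | Treatment Services Review, FRPN engagement v1, v2 and v3, Measure of Contact | 5 |

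4 + 5 + 5 = 14. The last five do not exist at randomization, so they can be neither urn variables nor baseline moderators.

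**Figures in the plan.** There is none to reproduce. The documents give no effect size, SD, power or dropout for any outcome. What follows is an illustration.

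**Inputs.** From the documents: 60 fathers (Sample Size); p below .10 counted as significant (SAP). Assumed: 1:1 allocation, so n = 30 per arm; two-sided test; no dropout; true effect d = 0.5 SD; correlation r between the baseline covariate and the outcome of .3, .5 or .7.

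**Precision at one follow-up visit, in SD units.**
- Without a covariate: SE = √(2/30) = 0.258.
- With a covariate: SE = 0.258 × √(1 − r²).
- Power = Φ(d/SE − 1.645), plus a negligible opposite tail.
- Detectable difference at 80% power = (1.645 + 0.842) × SE.
- Unadjusted sample size of equal worth = 60/(1 − r²).

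| Covariate | SE | d/SE | Power | Detectable difference | Equivalent N |
|---|---|---|---|---|---|
| None | 0.258 | 1.936 | 61.5% | 0.64 SD | 60 |
| r = .3 | 0.246 | 2.030 | 65.0% | 0.61 SD | 66 |
| r = .5 | 0.224 | 2.236 | 72.3% | 0.56 SD | 80 |
| r = .7 | 0.184 | 2.712 | 85.7% | 0.46 SD | 118 |

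If only 24 per arm are analysed, power is 53.5% without a covariate and 56.8%, 63.9% or 78.2% with one.

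**Chance imbalance.** For a baseline variable that the urn does not balance, the difference between arms has a standard error of 0.258 SD. An imbalance of that size carries r × 0.258 into the outcome comparison: 0.08, 0.13 or 0.18 SD at r = .3, .5 or .7.

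**The model matters.** Suppose a baseline were added and analysed as a time point in the SAP's GEE slope test. Take weeks 0, 16 and 24, equal correlation r between visits, and an effect either growing linearly to 0.5 SD at week 24 or already 0.5 SD at weeks 16 and 24. The slope has standard error √[(2/30)(1 − r)/S], where S is the sum of squared deviations of the three weeks from their mean. Power is then 51% to 56% at r = .3, 63% to 68% at r = .5 and 82% to 86% at r = .7. At r = .3 this is below the 61.5% of the comparison with no baseline. The gains in the table need the baseline value as a covariate.

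**The case against.** The case against is strong on consequence. None of the five hypotheses concerns moderation (the fifth is mediation), and the SAP conditions on nothing measured after randomization. Engagement and contact appear in no hypothesis and no expected result. The named parenting outcomes sit in their own block of Table 1, where the questionnaires have baselines. The SAP expressly provides for outcomes measured only at the end, and with complete follow-up that comparison is unbiased under randomization. A baseline collected in residence would also be retrospective or would reflect restricted contact, so r may be low. All of this stands, and it limits the point to precision, chance imbalance and an undefined role for these scales.

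A reader might draw four stronger conclusions that the documents do not support.

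- **That the label biases the treatment effect.** An example can be built. If treatment raises week-16 engagement by .5 SD and an unmeasured trait correlates .5 with both engagement and outcome, the within-arm slope is .5 × .5 = .25. Adjusting for engagement then gives a spurious effect of −.25 × .5 = −.125 SD under a true null. But that is covariate adjustment for a week-16 value, not an interaction, and the plan contains neither.
- **That the urn is faulty.** Its variables are not listed, nine of the 14 rows have baseline values it could use, and nothing says the other five were meant for it.
- **That no prior information exists.** This is true only of the instruments themselves. The interest form records contact frequency, and the Father Interview is given at baseline, though its content is not described.
- **That the two quizzes share the defect.** Both have baseline values. Expected Results treats that knowledge as an outcome, so only their filing needs clarifying.

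**Conclusion.** The point holds as one of precision and clarity. Five of the 14 Moderators rows are post-treatment measures with no stated analytic role, and no covariate is planned for the engagement and contact comparisons. The planned comparison is valid but less precise than it need be, and it leaves chance differences on entry uncorrected.

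The size depends on r, which the documents do not give. At r = .3 the gain is small (61.5% to 65.0% power). At r = .7 it is large (to 85.7%). These figures also rest on 1:1 allocation, a two-sided test, full follow-up, a 0.5 SD effect and a baseline-as-covariate model. A single contact-frequency item may correlate less with the outcome than the full scale would. The precision argument applies to engagement and contact. The Treatment Services Review is service use, not a fathering outcome, and needs only the correct label.

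**What to change.** 1. In Table 1 and the SAP, name the three engagement scales and the contact measure as secondary outcomes and the Treatment Services Review as service use. State that the urn and any moderator analysis use baseline variables only, and list the urn variables. File the two quizzes with the outcomes. This costs only an edit.
2. In the generalized linear models for week-16 and week-24 engagement and contact, prespecify adjustment for the contact frequency on the interest form. The data are already collected; the cost is coding one variable and one degree of freedom or a few.
3. Where enrolment still permits, give the engagement and contact scales at baseline with reference to the period before admission, with an indicator for expectant fathers, who have no baseline value. Enter the baseline score as a covariate in the generalized linear model, not as a time point in the GEE slope test. This lengthens a baseline interview already put at about 2 hours for men; the documents do not allow the added time to be estimated. The SAP is dated 2019 and written in the past tense, so this step may no longer be possible. Steps 1 and 2 do not depend on it. If the analyses have already been run, the adjusted comparison should be reported as added afterwards.

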The PI, co-investigator [name], and study coordinator will be the only ones who have access to the data, and data will be stored in locked file cabinets and on password protected computers. Data will be analyzed in aggregate to investigate study hypothesis (stated above).

Urinalysis Data Collection

To ensure urine screening data is available for all participants, including those who are no longer receiving services and providing urine samples at Westcare, Inc., or Salvation Army, any participants who have not given urine drug screens at Westcare Inc. or Salvation Army within a week of the post-treatment and 3 month follow-up assessments, Integrated iCups from Instant Technologies will be used for urine drug screening at the time of their assessment interviews. RAs will provide clean test cups taken from the packaging just prior to collection. Participants will be asked to provide the urine sample at the end of the assessment session. They will go into a private bathroom at the location of the interview. They will be instructed to place the sample in the cup and close it. RAs will wear rubber gloves when handling test samples. They will immediately read the urine test results by peeling the test panel on the side of the cup and reading the results. They will document the results on the Urine Screening Form. The urine sample and rubber gloves will be immediately disposed of in the waste bin at the location.

Sample Size

The study will be recruiting 60 male participants that are in a 6 month residential treatment, their female co-parents (youngest child's mother) and their youngest child for a total sample of 180.

Study Population

Sixty male participants of the WestCare Community Involvement Center or the Salvation Army Adult Rehabilitation Center who are residents.

Inclusion criteria: 1. Is the father (biological or adoptive) of a child under 15 years old (including an unborn fetus expected in the next 6 months); 2. Reports some verbal or physical aggression in his current or former co-parenting relationship; 3. Is diagnosed with substance use of alcohol, cocaine, amphetamines, opiates, marijuana at the time of intake at Westcare or Salvation Army.

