Department of Mental Health Law and Policy

Risks

The risks of this study are minimal. Participants may find it difficult to talk about stressful events that have happened to them and their families. They may experience some discomfort answering questions or talking about these things. Participants will be allowed to withdrawal from the study at any time. Participants may request a short break or discontinue any questionnaire at any time. If the child seems distressed or does not want to participate during play sessions, they will be discontinued. Additionally, male participants will be receiving residential treatment at WestCare or Salvation Army and have an individual therapist at the facility in addition to individual sessions as part of the research program. The support of the residential program and their individual therapist will provide them with support if discomfort arises at any time during the study.

Risk to female collateral informants is also minimal. Men are enrolled in residential substance abuse treatment so are not in the community or living with their families at the time of enrollment and the bulk of the study. Female co-parents will be contacted individually and safety of her participation will be assessed. If she feels her participation will put her at any risk for retaliation or violence by the father, she will not be enrolled. Prior to initiating co-parent treatment sessions with both partners for those in the FFC group, the clinician will assess the safety of the co-parent and ensure both want to participate. If significant symptoms or difficulties of female co-parents are revealed, this information will be reviewed with the study co-investigator, [name], and appropriate referrals will be provided to mothers who participate in the study. Mothers will be interviewed individually and confidentially on different dates and locations from the fathers in the study.

A. Behavioral therapies

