Psychological risks are minimal and not different from those of equivalent non-study psychotherapeutic interventions. For the treatment condition, frequent monitoring (at least weekly) of the participants' clinical status by the therapist and research staff will ensure identification and withdrawal from the study of participants who show significant psychological or symptomatic deterioration. If a participant shows significant symptomatic deterioration such that they are a danger to themselves or others or are in need of crisis intervention, the study clinical consultant, [name], a licensed clinical social worker and certified addiction counselor, will assess the client in consultation with the participants primary counselor or clinical director at Westcare or Salvation Army. A determination will be made about whether a higher level of care is needed beyond what is provided in the residential treatment setting. If significant symptoms or difficulties of female co-parents are revealed, this information will be reviewed with the study PI, [name] and co-investigator [name], and appropriate referrals will be provided to mothers who participate in the study.

B. Rating Scale and Questionnaires and ATSS Task.

To participate in this study, subjects are asked to complete various forms and questionnaires during their initial enrollment and post-treatment. All of the questionnaires are non-invasive and standardized and should add no risk to the subjects. They have been used in previous research with this population. The major disadvantage is the time taken to complete them. The ATSS paradigm has been used with the study population by the PI in her previous pilot studies and by others doing IPV research without adverse events. We will follow practices typically used with laboratory anger and distress tasks to debrief participants. As stated above, research assistants will guide participants in a relaxation session including guided imagery and deep breathing to ensure men are calm and not leaving the sessions aroused, distressed or angry. In the event that a participant remains agitated following the implementation of diaphragmatic breathing and a guided imagery scenario, the RA will contact the study clinical consultant, [name], Westcare, or Salvation Army clinical director to assess risk and next steps.

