Our past experience with these measures indicates that they are acceptable to patients. The initial baseline assessments for the study will take approximately 2 hours for completion for men and 1 hour for women. Post-treatment assessments will take approximately 1 hour for completion. A research assistant will meet with the patients independent of their clinician and conduct all assessments. Only patients' code numbers will be recorded on the forms themselves to protect confidentiality.

Benefits

Participants will receive an individual intervention to address parenting and co-parenting. As such, their mental health, physical health, and familial functioning may improve as a consequence of participation. Furthermore, this research will inform interventions for fathers with substance abuse and violence histories in residential treatment, enabling us to better treat these problems.

Compensation

Male participants in both the FFC Program and the Dads 'n' Kids Program will receive \$35.00 for their post-intervention interview at week 16 and will be paid \$50.00 for completing the 3 month follow-up interview with the research assistant. Female co-parents will receive \$25.00 for completing a baseline assessment and \$50.00 for completing a 3 month follow-up interview with the research assistant.

Human Subjects Considerations

Informed Consent

The P.I. and study coordinator will give flyers to the WestCare and Salvation Army staff, who will distribute them to male residents at intake into the facilities. They will be provided a screening sheet to complete and turn in if they are interested in participating. Volunteers who meet the study criteria will be taken on a first come - first serve basis. The study coordinator will then set up confidential meetings with volunteers individually to obtain informed consent. Consent forms will be given to participants and reviewed verbally by the study coordinator. Consents will clearly outline confidentiality and the limits that apply (see below). Potential participants will be allowed to ask questions at this time and take as long as necessary to give consent.

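### Men who deteriorate are withdrawn from the study with no stated further assessment, so outcome data may be lost because of worsening; the likely bias is modest and the fix cheap

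*Protocol*

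**What the plan says.** The rule is in the protocol under Risks, A. Behavioral therapies. The sentence opens "For the treatment condition, frequent monitoring (at least weekly" and goes on to say that this monitoring "will ensure identification and withdrawal from the study of participants who show significant psychological or symptomatic deterioration". A separate clinical step follows for men in crisis: "A determination will be made about whether a higher level of care is needed beyond what is provided in the residential treatment setting". Nothing there says whether research assessments go on after withdrawal.

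Other relevant places:

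- **Protocol, Study Design.** "Fathers in each treatment group will meet individually with their assigned therapist once per week for 50-60 minutes of treatment".
- **Protocol, Table 1.** DERS and STAXI are taken at baseline and weeks 12, 16 and 24, with no monthly mark. CTS2, from father and mother, is taken at baseline and week 24 only.
- **Protocol, Urinalysis Data Collection.** Study urine screens at the post-treatment and 3-month assessment interviews are meant to cover all participants, "including those who are no longer receiving services and providing urine samples at Westcare, Inc., or Salvation Army".
- **Protocol, Risks, B. Rating Scale and Questionnaires and ATSS Task.** "A research assistant will meet with the patients independent of their clinician and conduct all assessments".
- **SAP, Data analysis Plan.** Outcomes measured two to five times are analysed by GEE in intention-to-treat and per-protocol samples, with p below .10 counted as significant. Time is continuous in weeks when there are three or more measurements. No missing-data method, weighting or missing-data sensitivity analysis is given.

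**The concern.** Unweighted GEE in general needs missingness to be unrelated to the outcome, given the covariates in the model. A rule that removes men because they got worse breaks that condition. It also does so in a way that modelling cannot easily repair. A man withdrawn before week 12 leaves only a baseline DERS and STAXI score, so the data contain no trace of his decline. The intention-to-treat and per-protocol samples would lack the same scores, so agreement between them would not reassure.

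Hypothesis 2 concerns emotion regulation and related measures, and the pilot seeks an intervention signal on them. If one therapy makes more men worse, those men leave the estimate and the harm is understated. Completion rates would show that men left, but not that they left because they deteriorated.

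**Working it through.** **1. Is there a figure in the plan to reproduce?** No. The documents give 60 men but no effect size, SD, dropout rate or deterioration rate. Every size below rests on assumptions.

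**2. Which arms does the rule cover?** The text does not settle it.

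- *Both arms:* the section concerns behavioral therapies in general; each group has weekly therapist sessions; Study Design uses the plural, treatment conditions, for the two arms; and Risks names FFC when it means FFC only ("Prior to initiating co-parent treatment sessions with both partners for those in the FFC group").
- *FFC only:* the rule uses the singular, and Study Design calls parent education (PE) the comparison condition.

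**3. Model assumed.** There are 30 men per arm and visits at t = 0, 12, 16 and 24 weeks. Higher scores are worse.

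Y = b + (m + s)·t/24 + e, with Var(b) = 0.5, Var(e) = 0.5, SD(s) = 0.7, mean change m = −0.3 before any arm effect.

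The baseline SD is √(0.5 + 0.5) = 1, so results are in baseline SDs. The analysis is exchangeable GEE with arm by continuous time and robust standard errors. The contrast is the arm difference in change at week 24; negative favours FFC. Withdrawn men keep baseline only. The worst k of 60 men are withdrawn, ranked on a deterioration score that correlates 1.0 or 0.5 with the man's true slope. There were 4,000 runs per case, with Monte Carlo SE 0.005.

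**4. Standard error by hand.** In units of 24 weeks the visits are 0, 0.5, 0.667 and 1. Their mean is 0.542 and their sum of squared deviations is 0.521. With complete data the variance of one man's fitted slope is 0.7² + 0.5/0.521 = 0.49 + 0.96 = 1.45. The SE of the contrast is √(2 × 1.45/30) = 0.31, which matches the simulated 0.31.

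**5. Rule applied to both arms.**

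| Case (correlation) | All followed | 2 of 60 out | 3 of 60 out | 6 of 60 out |
|---|---|---|---|---|
| Harm: 3 of 30 FFC men worsen by 1.5 SD, true +0.15 (1.0) | +0.140 | +0.066 | +0.045 | +0.027 |
| Same harm (0.5) | +0.140 | +0.115 | +0.119 | +0.090 |
| Benefit: true −0.50 (1.0) | −0.498 | −0.435 | −0.412 | −0.376 |
| Same benefit (0.5) | −0.498 | −0.481 | −0.480 | −0.470 |

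The harm shifts run from 0.140 − 0.119 = 0.02 to 0.140 − 0.027 = 0.11. The benefit shifts run from 0.498 − 0.481 = 0.02 to 0.498 − 0.376 = 0.12. At correlation 1.0 the chance of p < .10 for the benefit falls from 49% to 42%, 40% or 35%. At correlation 0.5, a normal approximation with SE 0.31 gives about 45% to 46%.

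With no true difference, the estimate stays at −0.009 to +0.002 (+0.006 with nobody withdrawn), and p < .10 in favour of FFC occurs in 5% to 7% of runs (6% with nobody withdrawn).

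**6. Rule applied to FFC only, no true difference.** With 1 of 30 withdrawn the estimate is −0.048 (correlation 1.0) or −0.024 (0.5). With 3 of 30 it is −0.129 or −0.065. In a separate run a true −0.50 was estimated at about −0.63.

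**7. Heavier withdrawal as a stress test.** A second simulation withdrew men once their change crossed a threshold.

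- *Both arms:* a true −0.60 was estimated at −0.45 to −0.52 (2–9% of FFC and 13–29% of PE men withdrawn), and a true +0.60 at +0.41 to +0.51 (23–44% and 5–16%).
- *FFC only:* +0.60 was estimated at +0.28 to +0.45 (22–46% of FFC men withdrawn), and −0.60 at −0.61 to −0.67.
- *All men followed:* the estimates were within about 0.01 of the truth.

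The directions agree with steps 5 and 6. No document supports withdrawal rates at the upper end of these ranges.

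**The case against.** The strongest reply is that the loss of scores is inferred. The source is one sentence in a human-subjects section, not a follow-up rule, and it never says that interviews end. The urinalysis section also ties screening of men who have left facility services to assessment sessions at which Table 1 schedules DERS and STAXI, so the protocol does expect to interview some men after they leave. Both points stand. But leaving a facility's services is not withdrawal from the study, and that section does not mention the second group. Mothers' reports and court records may also survive; neither measures the father's emotion regulation or anger.

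The reply on size also stands. Correlation 1.0 is a ceiling, because therapists watch general clinical status and not DERS or STAXI. A harm of 0.15 SD would be hard to see even with full follow-up: 0.15/0.31 = 0.48, which gives p < .10 in the harmful direction about 12% of the time. At the 0.09 to 0.12 SD estimated under correlation 0.5 it is about 9% to 10%.

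A reader might infer that the rule manufactures a benefit for FFC, or that it always shrinks one. Neither holds in general. One rule in both arms creates no false benefit when the therapies are equal. Shrinkage needs withdrawal in both arms; under the FFC-only reading a benefit is slightly enlarged.

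**Conclusion.** The point holds in limited form. The protocol words the rule as withdrawal from the study, no provision keeps these men in assessment, and the SAP's GEE has no method for data lost through worsening. Harm can be understated under either reading of the arm wording; the effect on a true benefit depends on which reading is meant.

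The plausible shift is about 0.02 to 0.13 SD, or 0.02/0.31 = 6% to 0.13/0.31 = 42% of one standard error. This assumes the variances above, 1 to 6 of 60 men withdrawn, and withdrawal before week 12. The true number is not given and may be zero.

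A reader might go further and conclude that the GEE certainly has no later scores for these men, or that the trial's conclusions would be overturned. The documents do not support either: the end of assessment is the plain reading but is not stated, and the shifts are well inside sampling error. It is worth correcting because deterioration by arm is something a pilot in men with recent partner violence should be able to show.

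**What to change.** **Protocol, Risks, A. Behavioral therapies.**

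1. Reword so that significant deterioration stops the study sessions and triggers clinical referral, while the man is still offered the week 12, 16 and 24 assessments if he agrees and it is clinically safe. Safety is unaffected, because the level-of-care decision is already a separate step.
2. State that the same monitoring applies in both arms.

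**Reporting.**

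3. Give, by arm, the number withdrawn for deterioration or moved to a higher level of care.

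**If follow-up is already complete**, as the SAP's past tense suggests, items 1 and 2 no longer apply. Report the counts and, if any such men lack scores, consider an optional sensitivity analysis for DERS and STAXI. It would set their week-24 change worse than the observed mean in their arm by d = 0.5 to 1.5 baseline SD. The contrast then moves by (FFC share − PE share) × d. For 3/30 against 0/30 that is 0.05, 0.10 and 0.15 SD at d = 0.5, 1.0 and 1.5; equal counts give 0. Since the counts fix the shift, the counts matter most.

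**Cost.** Two sentences, one line of counts and a few extra visits by a research assistant who already works independently of the clinician. Some men will decline. The counts will be descriptive only: 3/30 has an exact 95% interval of 2% to 27%, 0/30 reaches up to 12%, and the two compared give Fisher p = 0.24.
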